#### **4. Criteria for Inclusion of Subjects:**

Patient sample: The study eligible patient population includes adult patients over 18 years of age diagnosed with AJCC Stage I-III incident breast or colorectal cancers AND with one or more of the following highly prevalent ambulatory-sensitive chronic conditions (diabetes, hypertension, chronic lung disease, chronic kidney disease, depression, or heart disease). We will exclude patients with in situ cancers (Stage 0) and those with metastatic disease (Stage IV).

Usual care pre-intervention sample: Our sample of 1000 non-cancer patients will include those with multiple chronic conditions (as above) and at least one doctor visit in the previous 12 months.

For patient cognitive interviews, surveys and semi-structured interviews (Aim 2), we will apply the following additional eligibility criteria: ability to comprehend English or Spanish, and communicate with voice (to participate in interviews and telephone surveys). Patients with and without eligible cancers are interview candidates.

Provider sample: Physicians and clinical staff (nurse practitioners, physician assistants, nurses, etc.) will be eligible if they have current clinical responsibilities in Parkland oncology clinics, involved in colorectal or breast cancer care; the Parkland complex care team; and Parkland Community-Oriented Primary Care Clinics (COPCS) who manage patients with multiple chronic conditions.

#### **5. Criteria for Exclusion of Subjects:**

Patients with impaired hearing or speech, inability to speak to English or Spanish, and refusal to consent (patient survey only) will be excluded from this study.

#### **6. Sources of Research Material:**

Data for this study will include:

- 1) Electronic Health Record (patient demographics, cancer and comorbidity diagnoses, appointments and dates, lab results and dates, screening procedures including results and dates, smoking history, medications, cancer treatment data). For the retrospective component of the study, we will request the EMR data from 01/01/2010- 12/31/2016. An additional sample of patients without cancer, but with 2 or more chronic conditions and a doctor visit in the last 12 months as a comparator group.
- 2) Patient survey data about patient experiences of care - validated measures
- 3) Audio-recordings of patient and provider interviews will collect qualitative data about patient experiences of care
- 4) Field notes of structured observations of clinic workflow

#### **7. Recruitment Methods and Consenting Process:**

**To evaluate the system-level outcome,** we will use EMR data collected on approximately 1000 patients from the Parkland system. We will ask the IRB for Waiver of Consent and Waiver of HIPAA

Authorization for EMR review and extraction of outcome data, and to conduct a confirmatory audit of 50 patient records identified by the EMR algorithm for individual chart review to confirm our ability to accurately capture all complex, Stage I-III breast, colorectal cancer patients completing active treatment.

**To evaluate the patient-level outcome**, we will use the EMR-generated patient list to randomly select ~866 complex cancer survivors in order to survey at least 402 after their transition to the complex care team. Based on our prior research experience with contacting Parkland cancer patients, patients are able and willing to complete telephone surveys. Further, we can expect 55% of those eligible will participate (n~480); 12% will actively refuse, 13% will have a non-working number, and 20% will be unreachable. We will also request a Waiver of HIPAA Authorization to identify and invite patients, and to compare, subsequently, demographics of non-respondents with participants to examine selection bias. All patients included in the system-level and patient-level outcomes are Parkland patients of the study investigators.

*Cognitive Interviews.* Working with the Cancer Center's *Spanish Language Translation/Validation Resource*, we will conduct 15 cognitive interviews in English or Spanish with a sample of Parkland cancer patients who were diagnosed with cancer in 2014 or earlier. These patients will not be included in the analyses for Aims 2 or 3. This sample will be recruited from the Parkland cancer registry or the Community Health Registry (STU 112010-061). We will ask the IRB for a waiver of documentation of consent and waiver of documentation of HIPAA Authorization for these participants. Trained, bilingual staff will recruit potential participants by telephone, explaining the goal of the interview, and schedule an on-site interview to be conducted at UT Southwestern. At the interview, staff will review session purpose, solicit informed consent, and conduct a half-hour cognitive interview to ensure the survey is understandable by individuals with low literacy skills and culturally appropriate. We will also evaluate whether the English and Spanish versions are conceptually equivalent. Cognitive interviews will be digitally audio-recorded; no HIPAA or other identifying information will be retained in the interview transcript. Gift card in the amount of \$15 will be provided to interview participants as an acknowledgment of their time and effort.

*Patient telephone surveys.* Patients identified for telephone survey will be mailed an invitation letter on Parkland letterhead, as appropriate, requesting participation in a "project to improve patient satisfaction with continuing care for their existing medical conditions." The letter will provide a local telephone number parents can use to opt-out or ask questions. Letters will be in both English and Spanish. A few days after the mailing, patients who have not refused contact will be called by a bilingual research assistant (RA) who will explain the project, verify eligibility, obtain verbal informed consent and HIPAA authorization for EMR review, and conduct a 30-minute survey. Up to 6 attempts per month for 2 months (day and evening) will be made to reach patients. Token gift cards will be provided to survey participants as an acknowledgment of their time and effort, per IRB stipulations. Provision of incremental remuneration (gift cards of \$10, \$20, \$40) will be provided in appreciation of the participant's time. Bilingual staff will invite a subset of survivors and usual care patients (n=90) for follow-up interviews (see below). We will also endeavor to sample an additional 10 patients for interviews from among those who did not respond to the surveys to explore selection bias.

Patients will complete surveys three times by phone – prior to their initial visit with the complex care team (baseline), and twice thereafter at 6 and 12 months. In addition to the primary measure, patients

will also be surveyed for key patient-reported confounding variables, potential mediators and moderators. Patients who have completed at least one survey will be invited to participate in an additional survey to assess the impact of COVID-19 on their overall health and well-being, including understand the effects of social distancing, patients' physical, emotional, and mental health, financial impact, and coping. Patients will receive a \$20 gift card for their participation in the COVID-19 survey.

*Structured observations and provider interviews and focus groups:* For study procedures involving clinicians and staff, we will request a Waiver of Documentation of Consent from the IRB because signed consent forms would be the only written record of participation, observations and interviews will concern only professional roles and responsibilities and no personal personnel information will be collected. We plan to conduct approximately 40 hours of structured observation, to interview approximately 40 providers, and conduct 2 focus groups (10-20 providers). Providers will be sampled on the basis of their involvement in cancer treatment, primary care and morbidity management (diabetes, hypertension, depression, heart disease, asthma); they will be invited to interview by faculty investigators. We will describe study objectives and purpose of the interview then solicit oral informed consent. No PHI will be collected.

*Patient semi-structured interviews:* A subset of 90 survey responders, (plus 10 non-responders, n=100) patients will be invited to complete a telephone interview. Following the existing recruitment procedure, additional eligible patients who did not complete a survey will be identified using EHR data and will be invited directly to interviews. An additional subset of 40 patients will be invited to complete a telephone interview focused on their experience with COVID-19. Patients will receive a \$40 gift card for their participation in the COVID-19 interviews.

An additional subset of 15 colorectal and breast cancer survivors identified from the retrospective cohort data will be invited to participate in semi-structured telephone interviews. Eligible participants will be mailed an invitation letter on Parkland letterhead requesting participation in a "project to improve satisfaction with cancer care" with a toll-free number to opt out or to ask questions. Bilingual staff members will contact patients by phone to 1) obtain informed consent and HIPAA authorization to review the patient's EMR; and 2) conduct the semi-structured interview in the patient's preferred language (English or Spanish). The interview will last about 45 minutes to 1 hour, and will be audio-recorded. All interviewers will be trained by [name] and supervised by Drs. [name] and [name]. Gift cards will be provided to interview participants as an acknowledgment of their time and effort, per IRB stipulations. All data will only be accessible to authorized study personnel and members of regulatory agencies.

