**For the patient-level hypothesis,** the design is a repeated measures study with outcomes measured on the same patients at three time points; at baseline and 6 months, and 12 months after transition to the complex care team for each individual patient. We will use linear mixed models to estimate effects on change in scores. Through specification of fixed effects, the mixed model allows for control of confounding variables, and can account for sources of natural heterogeneity by adding random effects that are unique to a particular individual. We will test different covariance matrices for random effects and will choose the matrix yielding smallest Akaike information criterion or largest restricted maximum likelihood estimate. Residual analyses and plots will examine adequacy of the final model. We will use SAS Proc Mixed procedure for analysis. Retrospective data might be missing. If data are missing at random (MAR), a linear mixed regression model is appropriate to address the issues of repeated measures and missing data in longitudinal studies. If the missing data are not missing at random (NMAR), we will explore the missing data pattern and a technique such as pattern mixture model will be used to adjust for NMAR bias.

**Power/sample size:** Assuming intra-subject correlation of 0.7 and minimum detectable standardized effect size of 0.25 (standardized effect size = effect size/standard deviation), we will need 402 patients to attain 80% power at  $\alpha=0.05$  using proposed mixed-effects linear regression analyses.

**Aim 3: (Research Component) *Conduct an intervention mixed-methods evaluation of implementation of care coordination strategies.*** This is especially important for system interventions implemented in the context of real world settings as proposed in this application to: (a) describe how the system-level strategies are implemented; (b) elucidate contextual factors affecting implementation at system and patient-levels; and (c) identify alternate explanations for observed effects on outcomes to generate counterfactual inference. Gathering qualitative and quantitative data before, during, and after implementation will enable us to assess the factors that influence implementation at system- and patient levels. Data collection methods include structured observations, complex care team surveys and provider interviews, patient surveys and interviews, and EMR extraction.

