**Interviewing providers and focus groups** from primary clinics with high and low rates of survivors' referred to the complex care team will help identify "work-arounds" and protocols that impede or facilitate care coordination, e.g. primary and specialty physician communication. Providers (n=30), sampled based on their involvement in cancer survivor follow-up care and chronic disease management, will be invited to interviews which will assess perspectives on patient uptake and other perceived challenges and opportunities. The PIs will develop interview guides, train and supervise the team in conducting interviews. Focus groups (N=2) and additional provider interviews (N=10) will be conducted to understand provider perceptions and experience treating cardiovascular disease risk for cancer survivors.

**Epic EMR data Extraction will be used to characterize:** (1) visit patterns with the nurse coordinator; (2) the extent to which care coordination, disease management and referrals to specialty providers and receipt of referrals occur; (3) patients who do not receive appropriate follow-up services; (4) missed appointments or loss-to-follow-up; and (5) processes related to care coordination. A separate data extraction of 1000 non-cancer patients with multiple chronic conditions will allow us to analytically characterize the non-cancer comorbid patient population at baseline as a comparator. We will also recruit a small subsample of these for baseline pre-intervention surveys and interviews.

**Aim 3 Data analyses:** We will use NVivo 9.0 (QSR International, AUS) to collate and analyze qualitative data. Use of this software makes the analytic process transparent so that investigators can track evolving analyses. Research staff will transcribe field notes from structured observations and gather existing protocols and documents relating to care of complex patients to enter into the database. We will develop flowcharts depicting complex care and primary care team members' relationships, roles, responsibilities, and behaviors in relation to practice change. Drs. [name] and [name] will work with research staff to organize these source documents and develop a codebook relating data to practice change, behavioral and organizational theories. We will triangulate across diverse data sources, to understand how providers adapt the strategies to suit the Parkland

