If we remove participants who decline to participate in these surveys/interviews from the total EMR cohort, we risk a significant percentage of cancer patients with chronic conditions treated at Parkland. Removing EMR data for these individuals would result in selection bias and also adversely impact our power to detect an effect as a result of our intervention. Inclusion/exclusion criteria (a finite number of eligible patients) eliminate our ability to replace patients who would decline to participate.

Therefore, we are requesting to consent participants for survey and interview participation, and maintain a full waiver of HIPAA authorization for eligible patients to conduct the system-level analysis.

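### Selection bias from about 45% survey non-participation is to be checked on demographics and about 10 interviews only, although baseline EMR care data kept for decliners could test it further and reduce part of it

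*Combined protocol and SAP*

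**What the plan says.** Section 7 (Recruitment Methods and Consenting Process) plans to draw about 866 complex cancer survivors at random from the EMR list so as to survey at least 402. It expects 55% to take part, about 480 patients, and of the others "12% will actively refuse, 13% will have a non-working number, and 20% will be unreachable". A waiver is requested so that the investigators can identify and invite patients and also "to compare, subsequently, demographics of non-respondents with participants to examine selection bias". The same section will try to "sample an additional 10 patients for interviews from among those who did not respond to the surveys to explore selection bias".

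Section 3 (Study Procedures, Aim 2, patient-level hypothesis) covers missing survey data: "If data are missing at random (MAR), a linear mixed regression model is appropriate". If data are not missing at random, the missingness pattern is to be explored and a technique such as a pattern mixture model used.

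The EMR data are much richer than demographics. Aim 2 derives chronic-disease and cancer-surveillance scores and rates of emergency visits and admissions. Aim 3 characterises referrals and "missed appointments or loss-to-follow-up". Section 6 lists appointments, laboratory results and procedures. Section 10 (Procedures to Maintain Confidentiality) asks to "maintain a full waiver of HIPAA authorization for eligible patients to conduct the system-level analysis", so survey decliners stay in the EMR cohort. It argues that removing them would itself cause selection bias.

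**The concern.** The survey outcome is patient-reported care coordination. Age, sex and ethnicity may match between participants and non-participants while the groups differ in what is likely to shape such a score: missed appointments, emergency use, or poor receipt of recommended care. Of the 45 percentage points of expected non-participation, 33 (13 + 20) are patients who cannot be contacted by telephone. It is plausible, though the documents do not show it, that such patients are also harder to schedule and refer.

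Two things are at stake. A balanced demographic table could be read as evidence of no selection bias, which it cannot provide. And the estimated change in care coordination may not describe the sampled population, with no stated analysis showing how far it might move. The plan recognises this risk for the system-level analysis, yet does not use the same records for the survey, where these patients are actually absent.

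**Working it through.** **Inputs.** Section 7: 866 sampled, 55% participating, 12% + 13% + 20% not participating, at least 402 surveyed, 10 non-responder interviews. Section 3, Aim 2: standardized effect 0.25, intra-subject correlation 0.7, 402 patients, 80% power, alpha 0.05 (two-sided assumed).

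**The plan's own figures.**
- Non-participation: 12 + 13 + 20 = 45%. Participants: 0.55 × 866 = 476, consistent with about 480. Non-participants: 866 − 476 = 390. Ten interviews reach 10/390 = 2.6% of them.
- Sample size: 402 is reproduced by the formula for a time-averaged difference between two equal groups with three measurements. Per group, 2 × 7.849 × [1 + 2 × 0.7]/(3 × 0.25²) = 200.9, so 2 × 201 = 402. The design described is a single cohort, so precision is shown below on both bases.

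**Size of the bias.** Let p be the participation share. The mean change in the whole sample is p × (participants' mean) + (1 − p) × (non-participants' mean). Hence

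bias = participants' mean − whole-sample mean = (1 − p) × (participants' mean − non-participants' mean).

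Only a difference in *change* matters; a stable difference in level cancels. With 1 − p = 0.45:

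| Assumed difference in change | Bias | Share of 0.25 SD |
|---|---|---|
| 0.10 SD | 0.45 × 0.10 = 0.045 SD | 18% |
| 0.20 SD | 0.45 × 0.20 = 0.09 SD | 36% |

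For scale, take a simple baseline-to-follow-up change in 402 patients with correlation 0.7, in units of the score's SD. Its standard error is √(2 × 0.3/402) = 0.039 SD. The bias would then be about 1.2 to 2.3 standard errors.

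**Could the EMR comparison detect anything?** With 476 against 390 patients, the standardized difference detectable with 80% power is (1.960 + 0.842) × √(1/476 + 1/390) = 0.19 SD. That is about 9.6 percentage points on a guideline rate of 43%, the Background figure for colorectal cancer survivors, used here only as an illustration.

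**Could weighting help?** In a simulation with 55% participation, participation depended only on an EMR score (log-odds 0.3 to 0.8 per SD) that correlated 0.3 to 0.5 with the outcome. The unweighted bias was 0.04 to 0.16 SD. Weighting by the inverse of the true participation probability brought it to about zero, with a design effect of 1.02 to 1.15. This is a favourable case by construction, because nothing outside the EMR score drove participation.

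**Cost in precision.** With a design effect of 1.10, 402 patients count as 402/1.10 = 365. Under the two-group formula that matches 402, power falls from 80% to 76%, and 443 patients (402 × 1.10, rounded up) would restore it. For a one-group pre-post change of 0.25 SD, power stays above 99%.

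**The case against.** The strongest reply is that the plan does more than a demographic table, and much of it stands.

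- *Drop-out.* A reader might infer that nothing detects or corrects loss after baseline. That is not so: Aim 2 provides a mixed model under MAR and, otherwise, exploration of the missingness pattern and a pattern mixture model. That step is conditional on NMAR, which observed data cannot establish, but it exists. It does not help with patients who gave no survey at all.
- *Content of the mixed model.* A reader might infer that the MAR assumption rests on survey items and demographics alone. The documents do not say so. The model allows fixed effects for confounders, and survey participants are asked to authorise EMR review.
- *Attrition.* The gap from about 476 to 402 is about 16%, but it is headroom over a minimum. The plan states no drop-out rate, so this gap cannot be added to the bias.
- *Size and direction.* The 0.10 to 0.20 SD difference has no source in the documents. It would also be tempting to say that the result will look too favourable; that holds only if patients with worse change are the ones missing.
- *Other contact with non-responders.* Section 7 also allows further patients without a survey to be invited directly to interview, though not for the stated purpose of studying selection bias.
- *Scope.* The primary outcome comes from the EMR and keeps survey decliners, so survey non-response does not affect it.
- *Waiver.* The wording about non-respondents names demographics, and the full waiver is tied to the system-level analysis. Using decliners' clinical records for this purpose needs approval and should not be assumed.

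What remains is the initial 45%: no EMR-based comparison or weighting is stated for it.

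**Conclusion.** The point holds for initial non-participation in the patient-level survey. About 45% of those sampled are expected to be absent, the stated checks are demographics and about 10 interviews, and better baseline information on the same patients is to be held but has no stated role in testing or reducing the bias. The 45% is the plan's own expectation. The resulting bias of 0.045 to 0.09 SD, 18% to 36% of the 0.25 SD target, rests on an assumed difference in change of 0.10 to 0.20 SD with unknown sign. It also takes the average change over all sampled patients as the target, and the score's SD as the unit of the standardized effect. The documents do not support saying that drop-out is unaddressed, that the reported effect will be inflated, or that the system-level result is at risk.

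**What to change.** **Section 7.** Extend the non-response comparison from demographics to pre-baseline EMR variables: chronic-disease and surveillance scores, emergency visits and admissions, and missed appointments. Report it for three groups: never took part, took part then dropped out, completed all surveys. Never-participants have no baseline survey date, so define a common reference date, such as the date of selection for the survey. Extend the waiver request to cover this use.

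**Section 3, Aim 2 patient-level analysis.** Add a sensitivity analysis that weights respondents by the inverse probability of responding, estimated from those pre-baseline EMR variables and demographics, and report it beside the unweighted result. Adding EMR covariates to the mixed model is not a substitute: never-participants contribute no survey outcome, and the model would still describe change among participants. Do not use post-baseline complex-care visits in the weights or as covariates, because they measure exposure to the intervention under study.

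**Cost.** Ethics approval of the wider waiver, some additional analysis, and a slightly wider confidence interval (design effect 1.02 to 1.15 in the simulated cases). No new data collection is needed. Only bias linked to the EMR variables is reduced; dependence on unrecorded perceptions of care would remain, and the report should say so.
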